6.3 MEASURES TO MINIMIZE BIAS: RANDOMIZATION AND BLINDING

Participants will be randomized to receive either Pfizer-BioNTech vaccine or placebo on Day 1 in a 1:1 ratio at enrollment via block randomization. On Day 2, subjects will receive whichever of vaccine or placebo that was not given on Day 1. A randomization scheme will be generated by the NIAID Biostatistics Research Branch who will provide a randomized list of arm assignments to the NIH Clinical Center Pharmacy. The randomization code list will be maintained by the Investigational Drug Control Unit (IDCU) in the electronic Investigational Drug Management System (IDMS).

The participants, the clinical staff, and the study team will be blinded to the order of study vaccine assignments. The unblinded pharmacy staff is responsible for maintaining security of the assignments.

Intentional unblinding: Unblinding will occur after the last participant has completed Visit 1. There will be no emergency unblinding for CoFAR Grade 3 or lower reactions because allergic and anaphylactic reactions to the vaccine are expected and will be treated per standard clinical care, and it is not necessary to unblind to do so. However, if a CoFAR Grade 4 or higher systemic allergic reaction or other life-threatening AE occurs, then both the investigator and the participant will be unblinded. If a CoFAR Grade 4 or higher reaction occurs on day 1, then the participant will not receive the study intervention the next day (either placebo or vaccine).

To break a treatment blind, the principal investigator will request a participant's treatment assignment from the IDCU. If an emergency request for treatment assignment is made by an individual other than the principal investigator and the principal investigator is not immediately available, the request will be made to one of the physician associate investigators, who will then contact the IDCU or appropriate NIH pharmacy after-hours contact to obtain the treatment assignment. If a participant's study agent assignment is unblinded, the information will be provided to only the individuals needing it for treatment decisions; all attempts will be made to maintain the blind of the study team.

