9 STATISTICAL CONSIDERATIONS

The analysis will be primarily aimed at estimation and description. There is considerable uncertainty about the number of subjects that can actually be enrolled, so both the sample size rationale and planned analysis are written to take that uncertainty into account. There is no intent to write a formal Statistical Analysis Plan.

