9.1 STATISTICAL HYPOTHESIS

The primary goal is estimation of the primary and secondary endpoints, and estimation of the difference in endpoints between the active and placebo vaccines. Statistical hypothesis testing will be done to compare active versus placebo vaccines, but this is secondary to estimation.

The endpoints are as follows, and are defined in greater detail previously in the protocol (sections 1.1 and 3):

Primary Endpoint:

- Proportion with systemic allergic reaction to the active (ie, Pfizer-BioNTech) vaccine dose delivered in this study

Secondary Endpoints:

- Proportion with severe systemic allergic reaction to the COVID-19 vaccine dose delivered in this study
- Proportion with mild/moderate systemic allergic reaction to the COVID-19 vaccine dose delivered in this study
- Proportion with anaphylactic reaction to the COVID-19 vaccine dose delivered in this study
- Proportion with systemic allergic reaction to each study vaccination (i.e. active and placebo/pre- and post-crossover) by arm
- Proportion with more (or less) severe systemic allergic reaction to the COVID-19 vaccine dose delivered in this study than recorded reaction to the first full COVID-19 vaccine dose

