9.2 SAMPLE SIZE DETERMINATION

The goal is to enroll up to 100 subjects; however, realistically, it may only be possible to enroll a smaller cohort. The ability to recruit for this study will depend on the rarity of such allergic reactions in the population and the acceptability of repeat vaccination and a 4-day hospital stay among individuals who have had these reactions. Current data indicates an extremely low systemic reaction rate, although it is likely that the overall rate may be higher since individuals recruited for this study have a history of a systemic allergic reaction following administration of the first dose of the vaccine. In sum, the study will provide more precise estimates with greater enrollment; however, even if fewer than 100 subjects enroll, the resulting data will provide valuable new information.

Since the primary goal of the study is estimation, we present the following example exact confidence intervals as a function of varying sample size and varying outcomes to illustrate achievable precision of estimates. We present such confidence intervals for the primary endpoint,

and also estimation of the risk difference of active vaccine versus placebo vaccine. The difference between active and placebo can be estimated in 2 different ways: one compares the results in the randomized arms at the first shot; and the other compares results within a subject across the 2 study vaccinations, exploiting the crossover design. Tables below present a subset of example scenarios in the study.

Table 5: Exact 95% Clopper Pearson Confidence Intervals for Primary Outcome, by Sample Size and Proportion with Systemic Allergic Reaction to Second Dose

Total N	Observed Reaction Rate					
	.00	.20	.40	.60	.80	1.00
5	0-0.522	0.005-0.716	0.053-0.853	0.147-0.947	0.284-0.995	0.478-1
10	0-0.308	0.025-0.556	0.122-0.738	0.262-0.878	0.444-0.975	0.692-1
15	0-0.218	0.043-0.481	0.163-0.677	0.323-0.837	0.519-0.957	0.782-1
20	0-0.168	0.057-0.437	0.191-0.639	0.361-0.809	0.563-0.943	0.832-1
40	0-0.088	0.091-0.356	0.249-0.567	0.433-0.751	0.644-0.909	0.912-1
60	0-0.06	0.108-0.323	0.276-0.535	0.465-0.724	0.677-0.892	0.94-1
80	0-0.045	0.119-0.304	0.292-0.516	0.484-0.708	0.696-0.881	0.955-1
100	0-0.036	0.127-0.292	0.303-0.503	0.497-0.697	0.708-0.873	0.964-1

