As the sample size increases, precision in the estimate of the true proportion of subjects with a reaction to the second vaccine dose also increases. As an example, if the total N is 10, and there is .20 reaction rate (i.e., 2 react) to active vaccine, then the 95% CI for reaction rate is (.025, .556).

Table 6: Exact 95% Confidence Intervals for the Difference in Reaction Rate Between Vaccine and Placebo Arms on Day 1

Total N	Observed Reaction Rate per Arm on Day 1		
	1.00 Vaccine, .00 Placebo	.80 Vaccine, .20 Placebo	.60 Vaccine, .20 Placebo
6	0.082-1	-0.282-0.992	-0.554-0.889
10	0.383-1	-0.112-0.933	-0.268-0.858
20	0.663-1	0.127-0.862	-0.058-0.756
40	0.824-1	0.287-0.798	0.084-0.666
60	0.881-1	0.313-0.767	0.134-0.622
80	0.702-1	0.338-0.748	0.144-0.594
100	0.597-1	0.355-0.734	0.16-0.575

Note: If only 6 subjects are enrolled, a reaction rate of 80% in the vaccine arm corresponds to 3/3 reactions; a reaction rate of 60% in the vaccine arm corresponds to 2/3 reactions; and a reaction rate of 20% in the placebo arm corresponds 1/3 reactions.

Thus, if the total N is 20 with 10 on active vaccine on Day 1 and 10 on placebo, and 8 of those receiving active vaccine have a reaction and 2 of those receiving placebo have a reaction, the 95% CI for the excess reaction in active vaccine minus placebo is (.127, .862). Since this particular confidence interval does not include zero, this is also a demonstration that vaccines lead to excess reactions.

Table 7: Exact 95% Confidence Intervals for the Risk Difference Comparing each Individual's Vaccine Phase to Placebo Phase Response Using McNemar's Approach

Total N	Observed Reaction Rate per Treatment Phase		
	1.00 Vaccine, .00 Placebo	.80 Vaccine, .20 Placebo	.60 Vaccine, .20 Placebo
5	-0.044-1	-0.275-0.947	-0.369-0.853
10	0.338-1	0.04-0.878	-0.088-0.738
15	0.517-1	0.162-0.837	0.026-0.677
20	0.621-1	0.235-0.809	0.084-0.639
40	0.797-1	0.369-0.751	0.192-0.567
60	0.861-1	0.423-0.724	0.238-0.535
80	0.895-1	0.453-0.708	0.264-0.516
100	0.915-1	0.473-0.697	0.281-0.503

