9.4 STATISTICAL ANALYSES

9.4.1 General Approach

Most analyses will result in estimates of binary endpoints and will be presented as proportions and corresponding exact 95% confidence intervals.

Exploratory endpoints, such as mechanistic endpoints, will be presented as means with standard deviations and/or as medians and interquartile ranges. Graphical presentation may be useful.

While hypothesis testing is likely to be limited in scope, two-sided p-values with alpha=.05 will be used, with appropriate cautions regarding interpretation due to multiplicity.

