9.4.3 Analysis of the Secondary Endpoint(s)

Analyses to simple single proportion estimates will follow the same approach described for the primary endpoint.

Analysis of risk difference between active and placebo vaccines will be addressed in 2 separate ways. First, using only data from the first study vaccination, the risk difference will be estimated (proportion with systemic reaction in the active vaccine arm minus the analogue in the placebo arm) with an unconditional exact confidence interval. The second approach will exploit the crossover design (i.e., comparing each individual's active vaccine to placebo response), by estimating the risk difference using a McNemar's approach to an exact confidence interval.[\[34\]](#) While the McNemar's approach should be more precise than the group comparison approach at the first study vaccination, the potential for missing data on the second study vaccination, especially in the initial vaccine arm is not ideal. If there are such missing data, the second study vaccination will be imputed in the most extreme ways (i.e., smallest risk difference and largest risk difference) to see if the results are robust.

Hypothesis testing can be done for the active vaccine versus placebo risk difference. A Fishers exact test will be done when comparing the randomized arm at the first study vaccination. An exact McNemar's test will be done when comparing the within-subject differences. Approaches to missing data for McNemar's follow the estimation approaches.

A signed rank test will also be done to compare severity of reaction at the first vaccine (i.e., done prior to enrollment) to active study vaccine (where the difference in grade is the metric). Since that analysis assumes grade is linear, these data will also be analyzed using a purely ordinal approach to grade using a longitudinal GEE model with a cumulative logit link; this is effectively a generalization of McNemar's test, but for ordinal instead of binary data. Tabular data will also be presented.

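### On Day 1 the Fisher test is more conservative than the exact interval it accompanies and can contradict it; a p-value matched to the interval removes this, and two Table 6 limits need correcting

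*Combined protocol and SAP*

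**What the plan says.** Section 9.4.3 gives two procedures for the comparison at the first study vaccination. The risk difference is estimated "with an unconditional exact confidence interval", with no ordering of outcomes named. For the test, "A Fishers exact test will be done when comparing the randomized arm at the first study vaccination". Section 9.4.1 adds that "two-sided p-values with alpha=.05 will be used".

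Table 6 in section 9.2 illustrates the interval. Its worked example is 8 of 10 vaccine reactions against 2 of 10 on placebo, with interval (.127, .862). The text then reads that interval as a test: "Since this particular confidence interval does not include zero, this is also a demonstration that vaccines lead to excess reactions".

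On priority, section 9.1 states: "Statistical hypothesis testing will be done to compare active versus placebo vaccines, but this is secondary to estimation". The end of section 9.2 says the same of the active-placebo comparison. Section 9 closes off a later document: "There is no intent to write a formal Statistical Analysis Plan".

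**The concern.** An unconditional exact interval and Fisher's conditional test answer the same question with different reference sets, so they need not agree near the 5% boundary. Here the interval also serves as a test, because the text under Table 6 draws a conclusion from its excluding zero. A report could then show an interval above zero beside a Fisher p-value above 0.05. Someone would have to reconcile the two after seeing the data, with only a general ranking of estimation over testing for guidance.

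The paired crossover analysis seems to avoid this. Section 9.4.3 cites for it a methods paper whose title (reference 34) describes paired intervals compatible with the exact McNemar test. The Day 1 analysis has no such match. It is also the comparison free of the missing second-vaccination data that 9.4.3 worries about.

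**Working it through.** **Inputs.** Two-sided alpha 0.05 and exact 95% intervals (9.4.1); 1:1 allocation (6.3); the 21 cells and worked example of Table 6 (9.2). The true rates used in step 4 are assumptions.

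**1. Reproduce Table 6.** Each limit comes from inverting a one-sided 2.5% test, maximised over the nuisance rate. With n per arm and N = 2n, all v none is the most extreme outcome. Its probability at difference d is largest when the vaccine rate and one minus the placebo rate both equal (1+d)/2. The lower limit therefore solves ((1+d)/2)^N = 0.025, so d = 2 × 0.025^(1/N) − 1.

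| N | Printed lower limit, 1.00 v .00 | Formula |
|---|---|---|
| 6 | 0.082 | 0.081 |
| 10 | 0.383 | 0.383 |
| 20 | 0.663 | 0.663 |
| 40 | 0.824 | 0.824 |
| 60 | 0.881 | 0.881 |
| 80 | 0.702 | 0.910 |
| 100 | 0.597 | 0.928 |

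Five cells match to within 0.001. The last two do not, and they fall as N rises for the same observed split.

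Over the whole table, ordering outcomes by the one-sided Fisher mid-p with exact ties kept together reproduces 18 of 21 cells to within 0.001, including (0.127, 0.862). The exceptions are the two cells above and N = 10 at .60 v .20. In that cell 3/5 v 1/5 ties exactly with 4/5 v 2/5. Keeping the tie gives −0.305, and breaking it gives the printed −0.268.

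**2. Fisher p-values.** Equal arms make the two tails symmetric, so the two-sided p is twice the upper tail.
- 3/3 v 0/3: 2 × 1/C(6,3) = 2/20 = 0.10, the smallest value possible with 3 per arm.
- 8/10 v 2/10: 2 × (45×45 + 10×10 + 1)/C(20,10) = 2 × 2126/184756 = 0.023.
- 7/10 v 2/10, and 8/10 v 3/10 by symmetry: 2 × (120×45 + 45×10 + 10×1)/C(20,9) = 2 × 5860/167960 = 0.070.

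**3. Set against the intervals.**

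| Outcome | Lower limit | Fisher p | Agree? |
|---|---|---|---|
| 3/3 v 0/3 (Table 6) | 0.082 printed | 0.10 | No |
| 8/10 v 2/10 (worked example) | 0.127 printed | 0.023 | Yes |
| 7/10 v 2/10, 8/10 v 3/10 | 0.018 | 0.070 | No |

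The other 20 printed cells agree. At N = 20, 6 of the 55 outcomes with more vaccine than placebo reactions conflict. Every conflict runs the same way: the interval excludes zero and Fisher p > 0.05. No reverse case appeared at any Table 6 sample size. The conflicts in the table above hold under mid-p, Boschloo, pooled-score and raw-difference orderings.

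**4. Chance of conflict** (equal arms, mid-p ordering, exact binomial sums). At N = 6 only 3/3 v 0/3 conflicts, so the chance at 80% v 20% is 0.8³ × 0.8³ = 0.262.

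| N | 80% v 20% | 60% v 20% | 20% v 5% |
|---|---|---|---|
| 6 | 26% | 11% | 0.7% |
| 10 | 0% | 0% | 0% |
| 12 | 28% | 17% | 1.2% |
| 20 | 17% | 17% | 5.5% |
| 40 | 2% | 8% | 12% |

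**5. A matched test.** Take twice the one-sided unconditional p-value, maximised over the common rate. For 3/3 v 0/3 this is 2 × (1/2)^6 = 0.031, consistent with the interval. At N = 20 its maximum two-sided size is 0.042, against 0.013 for Fisher. Power is 80.5% v 63.5% at 80% v 20%, and 42.5% v 25.3% at 60% v 20%.

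**The case against.** The strongest reply is that the protocol has already settled the hierarchy. Sections 9, 9.1 and 9.2 all put estimation first, and 9.4.1 expects testing to be limited in scope and read with caution. The comparison is secondary, and no success or stopping rule uses its p-value. Divergence near the boundary is a known property of these two valid methods. This largely stands. A reader might infer that the plan leaves the priority open, or that pairing the methods is an error. The documents support neither: they imply that the interval leads, and what they lack is an explicit sentence for a conflict.

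The sentence under Table 6 concerns one particular interval, with which Fisher agrees. The only printed conflict is at 3 per arm, and the N = 20 conflicts are neighbouring outcomes that the protocol does not print. That also stands.

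The larger conflict chances use Table 6's rates as if true, but section 9.2 says only: "Tables below present a subset of example scenarios in the study". It also notes very low reaction rates in current data, though possibly higher in this cohort. Section 2.3.3 cites a case series with 20% immediate, potentially allergic symptoms at the second dose. With 20% v 5%, where the 5% is purely an assumption, the chance is small at low N. It does not vanish, reaching 12% at N = 40.

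Finally, naming an ordering does not by itself remove the conflicts, since they persist under all four orderings tried. The matched p-value is what removes them.

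**Conclusion.** The point holds as a modest refinement. Fisher is the more conservative of the two Day 1 procedures and can fail to reject where the interval excludes zero. A matched unconditional p-value is a better companion to the interval: at N = 20 it holds its level and gains 17 percentage points of power at 80% v 20% (80.5 − 63.5). The chance of conflict depends on the final N and on rates that the protocol does not know: at N = 20, about 17% for 80% v 20% and about 5% for 20% v 5%. These figures assume equal arms.

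The two Table 6 lower limits at N = 80 and N = 100 in the 1.00 v .00 column are wrong. They do not affect the conflict, because interval and test agree in those cells either way. A reader might also infer that the N = 10 limit of −0.268 is wrong. That is not supported, since it follows from breaking an exact tie and reflects a convention.

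**What to change.** In section 9.4.3, name the ordering for the unconditional exact interval. One-sided Fisher mid-p with a stated tie rule fits Table 6 best. Take the two-sided p-value from that same procedure in place of Fisher, so that p < 0.05 coincides with the interval excluding zero.

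Timing matters. Section 6.3 says: "Unblinding will occur after the last participant has completed Visit 1". Section 4.1 records that by 15 September 2022 only two participants still had a 5-month visit to come, so the blind may already be broken, though the documents do not say so. If it is, keep Fisher as the prespecified test. Report the matched p-value beside it, and label that p-value, the chosen ordering and any statement of precedence as post hoc. Record the date of the change relative to unblinding.

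In Table 6, change the 1.00 v .00 lower limits from 0.702 to 0.910 at N = 80 and from 0.597 to 0.928 at N = 100. Leave the N = 10 .60 v .20 cell unless the named tie rule changes it.

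The cost is two or three sentences, two table entries and the IRB review that the Statement of Compliance requires for any amendment. After unblinding there is a further cost: two p-values for one secondary comparison, with the matched one only supportive.

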9.4.4 Safety Analyses

The primary and secondary endpoints of this study are focused on safety and will be evaluated and analyzed as described above. Allergic reactions will be scored using the CoFAR Grading Scale for Systemic Allergic Reactions Version 3.0 and the Brighton Collaboration Criteria. Other

AEs following active vaccine administration are expected as described in Section 2.3.1, and will be assessed during the participant's ICU stay as well as the remote follow-up within 1 week post-discharge (Visit 2) and at the in-person follow-up visits (Visits 3, 4, and 6). Efforts will be made to record start and stop dates of all AEs (both allergic and nonallergic in nature), severity, relationship to the study intervention, and expectedness based on study intervention. If participants experience a CoFAR Grade 4 or higher reaction on Day 1, or any life-threatening adverse reaction related or unrelated to the study intervention, then no additional dosing will occur and participants will be followed per study protocol.

9.4.5 Baseline Descriptive Statistics

Baseline descriptive statistics will be presented in terms of proportions, means/medians, standard deviations/interquartile ranges. Unless enrollment is very limited in size, the baseline variables will also be presented by randomized arm.

9.4.6 Planned Interim Analyses

No formal interim analyses are planned.

9.4.7 Sub-Group Analyses

The baseline characteristics of the cohort will be described. If the number of enrolled patients is sufficient, endpoints will be analyzed in subgroups (e.g., gender; age; ethnicity; severity of reaction to original vaccine dose; menopausal status for female participants; presence, type, and severity of allergic diseases; laboratory assessments of allergic sensitization and inflammation; history of allergic reactions including cause, severity, and treatment required; presence, type, and levels of anti-PEG antibodies; history of prior SARS-CoV-2 infection; other medical comorbidities; medication use; presence of genetic variants that may influence response to vaccine including but not limited to hereditary alpha tryptasemia; level of inflammatory and immune markers at baseline).

9.4.8 Tabulation of individual Participant Data

Individual patient data may be listed, especially if enrollment is limited.

9.4.9 Exploratory Analyses

Baseline mechanistic endpoints and other potential risk factors including results of mental health and anxiety assessments as well as changes in these endpoints pre- and post-vaccine will be described and compared between those with and without systemic allergic reactions (and likewise for other allergic endpoints). Analyses will generally use Wilcoxon rank sum tests when comparing groups and signed rank tests when comparing within subjects (e.g., pre- versus post-vaccine), however parametric tests might be used if number of enrolled patients is sufficient.

The ability to do hypothesis testing and modelling of risk factors and changes in exploratory endpoints pre- and post-vaccine will depend on the number of subjects enrolled. The proportion of subjects who react to the study-administered booster dose (among those who receive it), will be computed along with the corresponding 95% confidence interval, using the Clopper-Pearson method.

